8. Use of the following medications prior to randomization or concomitantly during the study (the doses and durations of specific treatments which will classify a patient as a protocol violator, based upon either prior or concomitant use, will be defined after data are available for review, but prior to unblinding for the first efficacy interim analysis). Patients/data points will be excluded from the start of the concomitant medication onwards.
 - anabolic steroids or glucocorticoids (≥ 5 mg/day prednisone or equivalent),
 - oral bisphosphonates (including alendronate, risedronate, clodronate, etidronate, ibandronate, or tiludronate),
 - I.V. bisphosphonates (including zoledronate, ibandronate, pamidronate),
 - cathepsin K inhibitor,
 - cyclosporine,
 - fluoride,
 - strontium,
 - PTH,
 - phenytoin, chemotherapy, heparin, or growth hormone,
 - estrogen \pm progestin (excluding topical applications), raloxifene, lasofoxifene, or other SERM, tamoxifen, tibolone, or an aromatase inhibitor,

² The number of missed consecutive doses was increased from 4 to 12 because the lower number was deemed overly stringent, as it equaled only 1 month of therapy, compared to approximately 3 months for 12 doses. In addition, it was felt that overall compliance with study medication was of greater importance after the first 6 months of treatment, as the effects of odanacatib on bone mineral density and bone strength (and hence fracture risk) have been shown to be time-dependent. Lower compliance during the first 6 months of the study is less likely to have a negative impact on the overall treatment effect, as fracture rates during this time period are more likely to be influenced by the patient's baseline level of risk, and yet to be altered by treatment.

Product: MK-0822

33

Protocol/Amendment No.: 018-04

- vitamin A (retinol and/or its esters); beta-carotene use is permitted,
- vitamin D (excluding study-provided concomitant vitamin D)

Biochemical Markers and Indices of Calcium and Mineral Homeostasis

Patients will not be included in the biochemical marker analyses for one or more of the reasons listed above. In addition, for the biochemical markers of bone resorption (u-NTx, s-CTx), a value will be excluded from the analysis if the last dose of study medication prior to the value is taken >7 days prior to the value, and for biochemical markers of bone formation (BSAP, P1NP) if the last dose of study medication is taken >30 days prior to the value.

Indices of calcium and mineral homeostasis will be handled as bone formation markers (>30 days).

Datasets/Programs/Variables

The directory structure following Merck guidelines will be used for storage of the data manipulation programs, data analysis programs, output tables, graphical displays, and analysis datasets. Naming of datasets, programs and variables will be performed according to the guidelines for good programming practice.

Product: MK-0822

34

Protocol/Amendment No.: 018-04

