3.2.3.9.1 Discontinuation Rules

As in all clinical trials, patients will be discontinued from blinded study therapy if the investigator feels that the risk outweighs the benefit of participation for an individual patient. Additionally, the following discontinuation rules will be applied.

Product: MK-0822

26

Protocol/Amendment No.: 018-04

- If relationship of the adverse experience to study drug is demonstrated by de-challenge and re-challenge, and the adverse experience is considered severe in intensity, or is serious.
- If a patient has a normal lymphocyte count at baseline, and then during treatment, lymphocyte count falls below the lower limit of the normal range and remains below the normal range on at least 2 repeated measurements, at least 1 week apart, and lymphocyte count returns to the normal range after interruption of study drug.
- If a patient experiences excessive bone loss, defined as a loss at the lumbar spine or total hip of 7% or greater compared to baseline at any point in the trial.
- If a patient demonstrates:
 - Persistent elevations [$> 3 \times$ Upper Limit of Normal (ULN)] in aspartate aminotransferase (AST) or alanine aminotransferase (ALT) (2 consecutive readings at least 2 weeks apart) - OR -
 - Persistent elevations [$> 2 \times$ Upper Limit of Normal (ULN)] in total bilirubin (2 consecutive readings at least 2 weeks apart).
- If a patient begins a treatment regimen with a strong CYP3A4 inducer (e.g., rifampin [rifampicin], phenobarbital, barbiturates, carbamazepine, phenytoin, St. John's wort, nevirapine, efavirenz, etravirine) for a period longer than 6 months in duration.
- If a patient commences therapy with low-dose systemic estrogens for 6 months or more.
- If a patient begins treatment with bisphosphonates, strontium, or PTH, the SPONSOR must be contacted and blinded study therapy will likely be discontinued.

Patients will be followed for outcome through the end of the trial even if blinded study therapy is discontinued.

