3.4.5.2 Selected Nonserious Adverse Experiences

These selected non-serious experiences are also known as Events of Clinical Interest (ECI) and must be recorded as such on the Adverse Experience Case Report Forms/Worksheets.

Product: MK-0822

38

Protocol/Amendment No.: 018-04

Events of clinical interest for this trial include:

Persistent elevations [$> 3 \times$ Upper Limit of Normal (ULN)] in aspartate aminotransferase (AST) or alanine aminotransferase (ALT) (2 consecutive readings at least 2 weeks apart) or persistent elevations [$> 2 \times$ Upper Limit of Normal (ULN)] in total bilirubin (2 consecutive readings at least 2 weeks apart) as determined by way of protocol-specified laboratory testing or unscheduled laboratory testing.*

***Note:** These criteria are based upon available regulatory guidance documents. The purpose of the criteria is to specify a threshold of abnormal hepatic tests that may require an additional evaluation for an underlying etiology.

Rash and Skin AEs

During the phase IIb trial for odanacatib, the SPONSOR received information regarding an ongoing assessment of a cutaneous safety signal observed with the use of a non-Merck cathepsin K inhibitor balicatib [5]. The adverse experience has been described as “morphea-like, local skin thickening.” For that reason, serious or severe rash and adverse experiences suggestive of morphea will be closely monitored in the odanacatib program. All serious skin AEs, or severe (according to intensity rating) skin AEs, or skin AEs with skin thickening and hardening suggestive of morphea or systemic sclerosis will be promptly reported (within 24 hours) as Events of Clinical Interest. In the reporting of these adverse experiences, all associated information that is considered relevant (e.g. medical history, concomitant therapy, the appearance, distribution, and duration of the rash, any treatments employed, dermatology consultation notes generated, the results of any procedures performed as part of the work-up, and if available, photographs of the lesion, etc.) should be completely documented and submitted with the patient data. Skin cancers are not considered ECIs. In addition, the skin AEs with skin thickening and hardening suggestive of morphea or systemic sclerosis will undergo adjudication.

Skin AEs that do not meet the criteria for ECIs above (i.e. those that are non-serious, and non-severe, or not suggestive of morphea) will follow standard data entry cycle times.

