The “All Patients-as-Treated” (APaT) approach will be used, which includes all patients who were randomized to double-blind treatment and received at least one dose of study medication. For this analysis patients will be counted in the treatment group for the treatment they actually received: if patients received one dose of the medication they were randomized to, they will be considered in their randomization treatment group, only if they received none of their actual randomization treatment and received the other treatment they will be considered in the other treatment group.

For vital signs and laboratory safety endpoints the APaT approach will be used, including all patients who took at least one dose of double-blind study medication and had a baseline and on-treatment measurement. Missing data will not be imputed.

Clinical Safety

Summary statistics will be provided for the change from baseline at each on-treatment time point in weight, blood pressure and pulse rate, by treatment group. Height will be handled as an efficacy endpoint.

Laboratory Safety

The primary focus of laboratory data will be based, for each laboratory test, on the proportion of patients exceeding predefined limits of change from baseline and/or exceeding predefined values, at least once during treatment period, until 14 days after the last dose of double-blind treatment.

The predefined limits of change from baseline and predefined values are displayed in Table 1.

For those predefined limits characterizing a large increase from baseline and/or a large on-treatment value, a patient exceeding the predefined limit will be classified as “above limit.” For those predefined limits characterizing a large decrease from baseline and/or a low on-treatment value, a patient exceeding the **predefined limit will be classified** “below limit.” The proportion of patients exceeding the predefined limits will be presented for the treatment groups, together with the 95% confidence intervals on the difference between the treatments.

In addition to the analysis of predefined limits of change, the change from baseline at each of the on-treatment time points in laboratory tests will be summarized for each of the treatment groups. No tests will be performed on the laboratory data.

A listing of all laboratory tests performed is in the appendix.

Product: MK-0822

18

Protocol/Amendment No.: 018-04

Table 1

Predefined Limits of Change Definitions for Laboratory Tests

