Laboratory Test	Predefined Limit of Change
Hemoglobin	Decrease $\geq 10\%$ and $< LLN$ Increase $\geq 10\%$ and $> ULN$
Hematocrit	Decrease $\geq 10\%$ and $< LLN$ Increase $\geq 10\%$ and $> ULN$
WBC count	Decrease $\geq 20\%$ and $< LLN$ Increase $\geq 20\%$ and $> ULN$ Value $< LLN$
Estimated neutrophils count	Decrease $\geq 20\%$ and $< LLN$ Increase $\geq 50\%$ and $> ULN$
Estimated lymphocyte count	Decrease $\geq 20\%$ and $< LLN$ Decrease $\geq 20\%$ and $< 1.0 \times 10^3/\text{microL}$ Increase $\geq 50\%$ and $> ULN$ Absolute lymphocyte count $< 1.0 \times 10^3/\text{microL}$
Estimated eosinophil count	Increase $\geq 50\%$ and $> ULN$ Value $\geq 0.65 \text{ ths}/\text{mm}^3$
Platelet count	Decrease $\geq 20\%$ and $< LLN$ Increase $\geq 30\%$ and $> ULN$
BUN	Increase $\geq 50\%$ Increase $\geq 20\%$ and $BLN > ULN$
Serum creatinine	Increase $\geq 50\%$ Increase $\geq 20\%$ and $BLN > ULN$
AST	Increase $\geq 50\%$ and $> ULN$
ALT	Increase $\geq 50\%$ and $> ULN$
Serum alkaline phosphatase	Increase $\geq 30\%$ and $> ULN$
Serum sodium	Decrease $\geq 5 \text{ mEq/L}$ and $< LLN$ Increase $\geq 5 \text{ mEq/L}$ and $> ULN$
Serum potassium	Decrease $\geq 0.5 \text{ mEq/L}$ and $< LLN$ Increase $\geq 0.5 \text{ mEq/L}$ and $> ULN$
Serum phosphate	Decrease $\geq 30\%$ and $< LLN$ Increase $\geq 30\%$ and $> ULN$ Value $\leq 2.0 \text{ mg/dL}$ also using value $\leq 1.5 \text{ mg/dL}$
Serum albumin	$< 3.0 \text{ g/dL}$
Serum direct bilirubin	Increase $> 50\%$ and $> ULN$
Serum total bilirubin	Increase $> 50\%$ and $> ULN$
Serum magnesium	Decrease $> 0.2 \text{ mEq/L}$ and $< LLN$ Increase $> 0.2 \text{ mEq/L}$ and $> ULN$
Serum calcium	Value $< 8.5 \text{ mg/dL}$ Value $> 10.5 \text{ mg/dL}$ also using Value $< 8.0 \text{ mg/dL}$

Product: MK-0822

19

Protocol/Amendment No.: 018-04

Predefined Limits of Change Definitions for Laboratory Tests (Cont.)

Laboratory Test	Predefined Limit of Change
Serum corrected calcium	Value <8.5 mg/dL Value >10.5 mg/dL also using Value <8.0 mg/dL
ULN = Upper Limit of Normal. LLN = Lower Limit of Normal. BLN = Baseline (pretreatment) value.	

Analyses and Populations of the Interim Analysis

Specific safety tables provided for the safety reviews before the first formal interim analysis (70% hip fracture events) will be discussed by the DMC during the kick-off meeting and detailed in the DMC charter and will be similarly to those mentioned in 3.5.5.2.

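### No specified safety table counts patients by the liver thresholds that stop therapy and define the hepatic ECI (AST/ALT >3×ULN, bilirubin >2×ULN), so an excess of large elevations could be diluted

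*Protocol*

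**What the plan says.** **The analysis.** Appendix 6.7 (Laboratory Safety) says: "The primary focus of laboratory data will be based, for each laboratory test, on the proportion of patients exceeding predefined limits of change from baseline". The sentence goes on: "and/or exceeding predefined values, at least once during treatment period, until 14 days after the last dose of double-blind treatment". Table 1 then lists the limits. AST and ALT have one row each: a rise of at least 50% to a value above ULN. The row "Serum total bilirubin" requires a rise of more than 50% to a value above ULN, as does direct bilirubin. None of these tests has a predefined value, a multiple-of-ULN row or a combined row. The same appendix gives 95% CIs for the difference between arms and says that laboratory data will not be tested.

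**The management rule.** Section 3.2.3.9.1 stops blinded therapy on "Persistent elevations [$> 3 \times$ Upper Limit of Normal (ULN)] in aspartate aminotransferase (AST) or alanine aminotransferase (ALT" or on persistent elevations above 2×ULN "in total bilirubin (2 consecutive readings at least 2 weeks apart". Section 3.4.5.2 uses the same thresholds for the hepatic ECI. It explains that they "specify a threshold of abnormal hepatic tests that may require an additional evaluation for an underlying etiology".

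**The tiers.** Section 3.5.5.2 and Table 3-11 put skin ECIs in Tier 1, provided at least 4 patients in one arm have one. The hepatic ECI is named in no tier. A specific AE gets a between-group CI only at 1% incidence or more in an arm; below that it is Tier 3, with within-arm figures only.

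**Where the detail belongs.** Section 3.5 and the opening of Appendix 6.7 say that the details of the stand-alone SAP now sit in this protocol, so the gap cannot be assumed to be filled elsewhere.

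**The concern.** The height of elevation that the protocol treats as important for an individual patient is not the height at which it compares the arms. Under Table 1 a value just above normal counts the same as one many times normal, provided each has risen by half. If a drug effect consists of a modest number of large elevations, that number is added to a much larger background of minor ones. The absolute difference is unchanged, but its CI widens.

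Table 1 and the stop rule also do not nest. Table 1 requires a relative rise and the stop rule does not, so some patients taken off therapy would not be counted.

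The protocol does align other tests with thresholds of interest. Section 3.4.2 has lymphocyte counts below 1.0 × 10³/microL reported to the regulator, and Table 1 has a row at that value. Calcium, phosphate and eosinophils also have absolute-value rows. The liver thresholds do not.

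**Working it through.** **1. The plan's own safety figure.** Section 3.5.5.2 says that with equal arms the 95% CI always includes zero when each arm has fewer than 4 events. At a difference of zero, the Miettinen–Nurminen statistic is χ² = (p₁ − p₂)² / V. Here V = [2p̄(1 − p̄)/n] × 2n/(2n − 1), and the cut is 3.84.
- 3 v 0: χ² = 3.00, so the CI includes zero.
- 4 v 0: χ² = 4.00, so the CI excludes zero.
- No pair with both arms below 4 exceeds 3.84.

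The figure reproduces, and the same statistic is used below.

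**2. Dilution (illustration).** From the documents: 16,716 enrolled (Section 3.1.1.1) and equal allocation (Section 3.5.1), so n = 8,358 per arm. Assumed, because the protocol gives no hepatic event rates:
- 20 placebo and 60 odanacatib patients exceed 3×ULN, and all of them also meet the Table 1 limit.
- The whole excess of 40 lies above 3×ULN.
- 2%, 5% or 10% of placebo patients meet the Table 1 limit.

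The difference is 40/8,358 = 0.48 percentage points in every row, and Z = √χ².

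| Row | Placebo v odanacatib | Ratio | Z |
|---|---|---|---|
| >3×ULN | 20 v 60 | 3.00 | about 4.5 |
| Table 1, 2% background | 167 v 207 | 1.24 | 2.09 |
| Table 1, 5% background | 418 v 458 | 1.10 | 1.39 |
| Table 1, 10% background | 836 v 876 | 1.05 | 1.02 |

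Since no laboratory tests are planned, the CI is the relevant output. At 5% background it runs from about −0.2 to 1.2 points; for the >3×ULN row it runs from about 0.3 to 0.7.

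**3. A second set of assumptions.** Take 8,150 per arm (half of 16,300) and an excess again confined to values above 3×ULN. The chance that the 95% CI excludes zero is Φ(Δ/SE − 1.96), with SE = √[(p₁(1 − p₁) + p₂(1 − p₂))/n].

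| Assumed >3×ULN rates | >3×ULN row | Table 1 row, background 2% to 10% |
|---|---|---|
| 0.2% v 0.4% | 65% | 14% to 6% |
| 0.3% v 0.6% | 82% | 26% to 9% |
| 0.5% v 1.0% | 96% | 58% to 18% |

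**4. Patients whom Table 1 misses.** A value above 3×ULN with a rise below 50% needs a baseline above 3/1.5 = 2×ULN. For bilirubin above 2×ULN the baseline must be above about 2/1.5 = 1.33×ULN. Exclusion 17 requires AST/ALT above 3×ULN and bilirubin above 2×ULN together, so it does not bar an isolated raised baseline, although exclusion 12 lets the investigator exclude some such patients.
- ALT from 2.5× to 3.2×ULN is a rise of 3.2/2.5 − 1 = 28%.
- Bilirubin from 1.5× to 2.1×ULN is a rise of 2.1/1.5 − 1 = 40%.

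If persistent, both meet the stop rule and the ECI. Neither meets Table 1.

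**5. The adverse-event route.** 1% of 8,358 is 83.6, so a specific hepatic AE term needs 84 patients in one arm to get a CI, against 4 for a skin ECI. In the illustration, 60/8,358 = 0.72%. Even if all 60 were recorded under one term, it would be Tier 3, without a CI.

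**The case against.** **The patients are captured.** Hepatic ECIs are recorded on the AE forms. Meeting the rule stops therapy, and laboratory-AE discontinuations are Tier 2 with a CI. There are also listings of patients withdrawn for an AE, Kaplan–Meier plots for laboratory AEs, and Tier 3 counts at any incidence. This stands: the events are not invisible. But the outputs with a CI pool hepatic with other events, and none counts patients by threshold.

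**The threshold serves individual management.** Section 3.4.5.2 presents it that way, and skin events are in Tier 1 because of findings with another cathepsin K inhibitor. That is a fair reason not to require Tier 1 for the liver. It is no reason to leave the threshold untabulated.

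**The illustration is favourable to the point.** It puts the whole excess above 3×ULN. A general upward shift in ALT would also add smaller rises to the Table 1 row and would be diluted less. So the claim is that dilution could occur, not that it would.

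**Nothing is lost for good.** The values are collected, and Section 3.5 allows changes to other analyses to be documented in the study report. True, but a threshold chosen after unblinding carries less weight than one fixed beforehand.

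**Stronger readings to avoid.**
- A reader might infer that a liver signal prompted the amendment. The summary of changes reports only a regulatory request.
- A reader might infer that the DMC will not see these counts. Section 3.5.5.6 and Appendix 6.7 leave its tables to the DMC charter, and Appendix 6.4 gives it access to all available data.
- A reader might see a contradiction between six-monthly safety samples after Month 12 and a rule that needs two readings. There is none: flow-chart footnote 3 and Section 3.4.5.2 provide for unscheduled tests. When a repeat sample is taken is a clinical matter outside this point.

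**Conclusion.** The point holds as a gap in the laboratory safety analysis. The primary laboratory table uses a low relative limit for the liver tests, and no specified table counts patients by the thresholds that stop therapy and define the hepatic ECI.

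Two consequences follow. An excess confined to large elevations could be diluted: in the illustration Z falls from about 4.5 to 1.39, with a range of 2.09 to 1.02 over backgrounds of 2% to 10%. And patients with a raised baseline can meet the stop rule without being counted in Table 1. The second follows from the criteria alone. The first depends on assumed rates and on where the excess lies; the documents give no hepatic rates with which to narrow it.

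The documents do not show that a hepatic imbalance exists, or that it would go unseen. The case for the change is that the informative comparison can be specified now at almost no cost.

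**What to change.** Add these rows to Table 1 of Appendix 6.7:
- AST or ALT >3×ULN, as any single on-treatment value and as persistent under Section 3.4.5.2.
- Total bilirubin >2×ULN, in the same two forms.
- AST or ALT >3×ULN and total bilirubin >2×ULN in the same patient. This goes beyond the stop rule, which joins the two by OR, and is descriptive.

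Give counts and the 95% CI for the difference for each row irrespective of the 1% cut, because Table 3-11 otherwise gives predefined limits of change a CI only at 1% or more. Keep the existing rows, which remain useful for a general shift. Name the hepatic ECI in Table 3-11, with a between-group CI that does not depend on 1% incidence.

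The cost is a few table rows from central-laboratory data already collected and one entry in Table 3-11, fixed before unblinding. No discontinuation threshold, visit or sampling rule needs to change.
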